8.2 Screening Exclusion Criteria

Patients are to be excluded from the study at the time of screening for *any* of the following reasons:

1. Pregnancy: due to the potential teratogenic effects of retinoids, pregnant women are NOT eligible;
2. Breast milk feeding by study patient is NOT allowed;
3. Health condition deemed to possibly interfere with the study endpoints and/or the safety of the patients. In case of doubt, the Investigator should consult with the Sponsor's medical representative;
4. Clinically abnormal renal function: serum creatinine $> 132 \mu\text{M}$ ($>1.5 \text{ mg/dL}$);
5. Clinically abnormal liver function: Total bilirubin $>1.5 \times \text{ULN}$ (in the absence of demonstrated Gilbert's syndrome), ALT and/or AST $> 2.5 \times \text{ULN}$;
6. Patients with plasma retinol levels below $0.7 \mu\text{M}$;
7. Known history of a severe allergy or sensitivity to retinoids (e.g. vitamin A, isotretinoin, etretinate), or with known allergies to excipients in the oral capsule formulation proposed to be used in the study;
8. History of organ transplantation;
9. History of alcoholism or drug abuse within 2 years before screening;
10. Presence of a cancerous tumor, active or in remission, treated or not, except squamous or basal cell carcinomas of the skin that have been treated and deemed resolved;
11. Presence of nyctalopia (also called night-blindness, which is the inability to see well at night or in poor light) or hemeralopia (the inability to see in bright light) at enrolment, or any other serious retinal, ophthalmological condition (eg: retinitis pigmentosa, choroidoretinitis, xerophthalmia, uncontrolled glaucoma);
12. Presence of serious dermatological conditions at entry, including inflammatory or xerotic pathologies such as psoriasis or ichthyosis;
13. Intake of chronic systemic steroids in the month prior to screening and during the study. Inhaled corticosteroids for treating asthma/rhinitis are allowed as well as systemic corticosteroids ($\leq 5 \text{ mg/day}$ of prednisone or equivalent or a higher loading dose tapered down in subsequent days) administered temporarily to control asthma exacerbations or pulmonary infections associated with bronchospasm (topical corticosteroids for dermatologic conditions may be allowed, subject to Investigator and Sponsor's representative authorization);
14. History of acute infections (viral/bacterial/fungal) within 5 weeks prior to randomization, of which 2 weeks minimum are prior to screening, whether or not treated and resolved. Exceptions are topical skin infections under treatment/treated with a local non-prescription antibiotic;
15. Presence of infection with *Burkholderia cepacia* (including all species within the *Burkholderia cepacia* complex group, and *Burkholderia gladioli*) in the 12 months prior to screening (resolution of previous episode confirmed by quarterly negative cultures for the 12 months prior to screening);
16. Patients with a confirmed diagnosis (as per the CFF diagnostic criteria) of Allergic Bronchopulmonary Aspergillosis "ABPA" and actively being treated with corticosteroids and/or antifungals agents;
17. Participation in another drug clinical trial within 30 days, meaning from the last study drug administration of the prior study (or a minimum of 5 elimination half-lives) prior to screening;
18. Any other clinically significant condition that is considered by the principal investigator as being susceptible to put the patient at greater safety risk, influence response to study product, or interfere with study assessments.

8.3 Withdrawal of Patients

Patients should be withdrawn from the study in the event of any of the following:

1. If a patient does not continue to meet eligibility criteria at baseline, the patient will be withdrawn prior to randomization;

2. Occurrence of a SAE deemed definitely or probably related to drug that is a life-threatening adverse reaction or one resulting in hospitalization;
3. If a patient withdraws consent during the treatment period, and more specifically consent to contribute additional outcome information, the patient shall be withdrawn from the study (although it is recommended that the investigator attempt to perform a Treatment Discontinuation Visit Evaluation). If the patient withdrawing consent to further treatment agrees to contribute additional outcome information, then the regular schedule of visits could be maintained, for safety and relevant outcome measures of efficacy.
4. If a patient is serially and persistently noncompliant with study procedures and/or visit schedules, the investigator or the sponsor may withdraw the patient from the study
5. A patient's treatment is unblinded by the Investigator.
6. If a female patient or a female partner of a male patient has a confirmed pregnancy (with the exception of a pregnancy resulting from *in-vitro* fertilization), this should be immediately reported to the Medical Monitor and Laurent Pharmaceuticals (within 1 working day of discovery) and the patient shall be withdrawn. Pregnancy, whether in a patient or in a partner of a patient should be followed up until conclusion, with an assessment of child health at birth.

The reason for patient withdrawal will be noted on the e-CRF. The investigator should attempt to follow patients withdrawn after first dosing until resolution of any adverse events, or at least 4 weeks after the last dose of study agent, or until completion of pregnancy. Upon withdrawal, no further dosing should be performed for these patients. Investigators shall make reasonable attempts to contact lost-to-follow-up patients for evaluation.

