8.4.1 Individual Patient Stopping Rule

The following should be used as a guide for the Investigator to determine if the study drug administration is to be interrupted based on toxicity (see Section 11.1.1.3 on Study Drug Action Taken, for more detail on documentation):

- A subject develops a medical condition that requires prolonged concomitant therapy with a prohibited medication or prolonged interruption of the study drug;

- Occurrence of a SAE that could be attributable to the drug (at least *probably* causality relationship), and causes discontinuation of study drug for more than 3 weeks;
- High and unexpected frequency and/or severity of “at least probably related” adverse events that in the judgment of the Investigator, requires withdrawal from the study.

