12 STATISTICAL ANALYSIS

A statistical analysis plan (SAP) will provide details of the methods of analysis to address all study objectives. The SAP may be amended during the course of the study, but will be finalized before the cutoff date for any analysis.

Data summaries by treatment group will be presented. For continuous variables, data will be summarized with the number of patients, mean, standard deviation, median, and minimum and maximum values by treatment group. For categorical variables, data will be tabulated in frequency tables to display the number and proportion of patients for each category by treatment group. Baseline assessments for each outcome variable will be defined as the last measurement obtained before the first dose of study drug except the baseline FEV₁ which will be the average of the screening and baseline best values, to reduce variability. Statistical significance will be set at the 5% level.

Diligent efforts will be made to prevent missing data in the study. For example, patients who discontinue the study treatment early or initiate medication changes (including those prohibited by the protocol) should still be followed for all regularly scheduled visits for safety and relevant efficacy assessments, or for a minimum of a 1-month follow-up. A clear distinction should be made between treatment discontinuation and study withdrawal. Efficacy assessments occurring after treatment discontinuation should not be included in the per-protocol analysis.

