3.14 Analysis of the Primary Efficacy Endpoints

The study will be considered successful if a statistically significant advantage for fenretinide over placebo is obtained for the absolute change in FEV₁ percent predicted from baseline to Week 24, as assessed in the ITT population. Confirmatory analyses will be conducted in the PP Population, Protocol-defined PEx Population and Overall PEx Population.

Values for percent predicted FEV₁ as well as their change relative to baseline will be tabulated by time point and descriptive statistics will be used. In the analysis of the primary efficacy endpoint, the absolute change from Baseline in FEV₁ percent predicted, including all measurements up to Week 28 (both during and after treatment measurements, including after treatment discontinuation) will be analyzed based on a mixed model for repeated measures, with the following specifications:

- The dependent variables will be all the absolute changes in FEV₁ percent predicted from Baseline to each time point, including Week 28;
- The fixed effects will be the treatment group, the visit and the treatment-by-visit interaction;
- The random effect will be the patient;
- An unstructured variance-covariance structure will be adopted as the default structure; alternate variance-covariance structures may be adopted as appropriate.
- The model will be adjusted for the following *à priori* stratification categories:
 - FEV₁ percent predicted determined at Baseline (<70% versus ≥70% predicted),
 - PEx frequency in the prior year (≤3 versus > 3 PEx episodes),
 - Co-administration or not of Kalydeco® (ivacaftor), Orkambi® (ivacaftor/lumacaftor), Symdeko® (ivacaftor/tezacaftor) or another commercially available CFTR modulator product (yes versus no);

- The difference between treatment means at each time point and its 95% confidence interval will be estimated.
- Stratum-specific estimates based on Least Square Means will be generated

The primary result obtained from the model will be the treatment effect at Week 24. The estimated mean treatment effect, a 95% confidence interval, and a 2-sided p-value will be generated.

The analysis will be repeated with the addition of the following covariates in the model:

- Baseline use of Trikafta (yes versus no);
- Effect of the pandemic confinement (pre versus post pandemic onset) (described in Section 3.14.1)

Alternative methods will be used if necessary due to data not meeting the standard requirements for the proposed analysis.

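### Protocol 8.3 takes some patients out of the study where 8.4 only stops their drug, so Week 24 FEV1 may be lost for reasons that could differ by arm

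*Protocol*

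**What the plan says.** Protocol 8.3 opens: "Patients should be withdrawn from the study in the event of any of the following". Six items follow.

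- Item 2 is "Occurrence of a SAE deemed definitely or probably related to drug that is a life-threatening adverse reaction or one resulting in hospitalization".
- Item 5 is "A patient's treatment is unblinded by the Investigator".
- Item 4, persistent noncompliance, is left to discretion: "the investigator or the sponsor may withdraw the patient from the study".
- Item 6 is pregnancy.
- Item 3 is the only one that provides for outcome data. A patient who withdraws consent to treatment but agrees to give further outcome information may keep the usual visits.

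For patients withdrawn after first dosing, follow-up runs "until resolution of any adverse events, or at least 4 weeks after the last dose of study agent", or to the end of a pregnancy. Section 8.3 gives these patients no spirometry schedule.

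Protocol 8.4 is a separate route: the patient comes off drug and is kept in the study. After a stop for toxicity or another safety reason, it asks for the planned visits or, as a minimum, one visit 4 weeks after the last dose. Section 8.4.1 is a guide for interrupting drug. It includes a serious adverse event at least probably attributable to the drug that halts dosing for more than 3 weeks. Its last bullet, however, speaks of adverse events whose frequency or severity, "in the judgment of the Investigator, requires withdrawal from the study".

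Protocol 12 asks that stopping treatment and leaving the study be kept distinct. It says that patients who stop early "should still be followed for all regularly scheduled visits for safety and relevant efficacy assessments", and the same sentence then accepts one month of follow-up as the minimum.

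SAP 3.14, like Protocol 12.4.1, fits a repeated-measures mixed model to all FEV1 up to Week 28, "both during and after treatment measurements, including after treatment discontinuation", and SAP 3.14 names the ITT population. Nothing is imputed. SAP 3.14.2 adds multiple imputation only when more than 5% is missing in each group. In the Schedule of Events the Day 189 column also serves as early termination and includes pulmonary function testing.

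**The concern.** By including FEV1 measured after treatment stops in the ITT population, the primary analysis in effect asks what happens to everyone randomized, whether or not they stay on drug. That question can be answered only if patients who stop are still measured at Week 24. Items 2 and 5 of 8.3 end participation for post-randomization events, and one of them depends on judged relatedness to the drug. Item 5 can also begin with a safety event, because Protocol 7.3.2 permits unblinding in an emergency.

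A site facing a hospitalizing, probably related event can follow 8.3 (out of the study) or 8.4 with 8.4.1 (off drug, still in the study) and be compliant either way. If 8.3 is followed before Day 161, the Week 24 value is lost although the patient did not refuse. If such losses fall more on one arm, and those patients do worse than their earlier values suggest, the estimated difference shifts.

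**Working it through.** **1. The plan's own figures.** The documents give no rate for withdrawals of this kind, so there is none to reproduce. The nearest figure is the sample size (Protocol 12.1: difference 4, SD 8, power 80%, two-sided 5%):

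n per group = 2 × (1.960 + 0.842)² × 8² / 4² = 62.8, so 63. An exact t-test gives 64. The plan states 60, at which power is 78.2% (normal approximation). That shortfall is a separate matter and does not bear on this point. The step to 136 does reproduce: 120 / 0.9 = 133.3, so 134, raised to a multiple of 8.

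**2. The passages side by side.**

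| Event | Protocol 8.3 | Protocol 8.4 / 8.4.1 | Later FEV1 |
|---|---|---|---|
| Definitely or probably related SAE, life-threatening or hospitalizing | Out of the study | Overlaps the SAE bullet of 8.4.1: drug interrupted | None scheduled in 8.3; under 8.4, planned visits or one visit at 4 weeks |
| Other unacceptable toxicity or adverse event | Not listed | Off drug, in the study; last bullet of 8.4.1 says study withdrawal | Planned visits or one visit at 4 weeks |
| Unblinding by the investigator | Out of the study | Not listed | None scheduled in 8.3 |
| Persistent noncompliance | Discretionary | Not listed | None scheduled in 8.3 if withdrawn |
| Consent to treatment withdrawn, consent to data kept | Usual visits may continue | Patient may stop drug | Available |

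The conflict lies in the first row and in the last bullet of 8.4.1. The unblinding row is a gap: nothing provides for outcome data. Separately, the one-visit or one-month minimum in 8.4 and 12 means that Day 161 is not assured on the drug-discontinuation route either.

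**3. What the imputation trigger would catch.** With 136 / 2 = 68 per arm, 5% is 3.4, so at least 4 values must be missing in both arms. A loss of 4 active (4/68 = 5.9%) and 2 placebo (2/68 = 2.9%) would not trigger it. SAP 3.14.2 also glosses the trigger as fewer than 57 patients per group with data, which is 0.95 × 60. Against 68 per arm that means at least 68 − 56 = 12 missing (17.6%) in each arm. On either reading a one-sided loss can pass. No departure from missing at random is specified.

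**4. Size, by assumption only.** Let f be the share of the active arm removed and e their true Week 24 effect. Suppose the model in effect credits them with 4. Then bias = f × (4 − e).

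| f (patients of 68) | e = 0 | e = 2 |
|---|---|---|
| 2% (1.4) | 0.08 | 0.04 |
| 5% (3.4) | 0.20 | 0.10 |
| 10% (6.8) | 0.40 | 0.20 |

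The 10% row equals the plan's expected maximum for dropout of every kind, if spread evenly over the arms. The standard error of the difference at 60 per group is 8 × √(2/60) = 1.46, so 0.20 points is 0.20 / 1.46 = 0.14 standard errors.

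**5. Power.** By the normal approximation with losses split equally, power is 83.0% with all 136, 81.9% with 4 lost and 80.7% with 8 lost.

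**The case against.** The strongest reply is that 8.3 and 8.4 are two deliberate routes, which is the very distinction Section 12 asks for, and that most tolerability stops go down the 8.4 route and stay in the study. Much of this stands:

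- Item 2 is narrow. The event must be definitely or probably related, and also life-threatening or hospitalizing.
- Noncompliance withdrawal is optional, and patients who keep missing visits would often lack Day 161 data anyway.
- The 4 weeks in 8.3 is a floor, not a limit.
- The early-termination column includes spirometry, and the model takes any measurement up to Week 28. That reading is not a Day 161 value, though, and neither document says which model visit it belongs to.
- SAP 3.4 reports discontinuation reasons by arm, so the pattern would at least be visible.
- In Phase Ib, with 15 patients, both serious adverse events were classed as unrelated. This points to a low rate, but the sample is too small to settle it.

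A reader might infer that Section 12 guarantees full follow-up and that 8.3 takes it away. The documents do not support that, because Section 12 itself accepts one month. What the reply does not remove is the overlap between item 2 and 8.4.1, the study-withdrawal wording in the last bullet of 8.4.1, and the absence of any outcome provision after investigator unblinding.

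**Conclusion.** The inconsistency holds on the text. Following 8.3 as written can lose Week 24 FEV1 for reasons that could be treatment-related and could differ by arm, in an analysis defined to include off-drug measurements and to impute nothing.

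Three stronger conclusions do not follow. It is not established that missing at random fails; it may not hold for these few patients. It is not established that the values are missing by rule for every listed reason, since noncompliance is discretionary. No bias of known size or direction can be stated, because the documents give neither a removal rate nor the outcomes of those removed. The model would also run without the off-drug data.

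The size is therefore unknown and probably small. The 0.04 to 0.20 points for 2% to 5% removed rests entirely on assumed f and e, and on all such removals falling in the active arm. It is a reason to tidy the protocol, not a threat to the trial.

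**What to change.** Reconcile Protocol 8.3, 8.4, 8.4.1 (including its last bullet) and 12 so that they agree on who stays in outcome follow-up. Leave every treatment-stopping criterion and the pregnancy provisions (8.3 item 6 and 11.1.3.1) exactly as they are. State that a patient who stops study drug because of a serious adverse event, toxicity or unblinding is still asked to attend the spirometry visits already in the Schedule of Events, at least Day 161, unless consent to further data collection is withdrawn. This extends what 8.3 item 3 already offers. It should also cover the one-visit minimum in 8.4 and the one-month minimum in 12, so that these are fallbacks and Day 161 is still sought.

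The cost is a protocol wording change and a few additional off-drug visits for each affected patient.

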11.1.1.3 Study Drug Action Taken

The investigator will classify the study drug action taken with regard to the AE. The action taken should be classified according to the categories shown below:

Classification	Definition
Dose Not Changed	Study drug dose not changed in response to an AE;
Dose Interrupted	Study drug administration interrupted in response to an AE;

Drug Withdrawn	Study drug administration permanently discontinued in response to an AE;
Not Applicable	Action taken regarding study drug administration does not apply. "Not applicable" should be used in circumstances such as when the investigational treatment had been completed before the AE began and no opportunity to decide whether to continue, interrupt, or withdraw treatment is possible.

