11.1.3.1 Serious Adverse Event Reporting

It is imperative that the safety desk be informed within 24 hours of an SAE so that reporting to the health authority can be met within the required time frame.

Because of the need to report to health authorities all serious adverse reactions in a timely manner, it is vitally important that an Investigator report immediately any adverse experiences which would be considered serious, even if the Investigator does not consider the adverse experience to be clinically significant or drug related. Should the Investigator become aware of an SAE (regardless of relationship to study drug) that occurs within 4 weeks after the last dose of the study drug, the SAE must be reported in accordance with the procedures specified in this protocol.

All SAEs that are not resolved by the end of the study, or that were not resolved upon discontinuation of the patient's participation in the study, are to be followed until the AE resolves, the AE stabilizes, the AE returns to baseline values (if a baseline value is available), or it is shown that the AE is not attributable to the study drug or study conduct. If a patient or a female partner of a patient becomes pregnant during the study, the patient will be removed from the study without receiving further study medication. Follow-up regarding the outcome of the pregnancy and any postnatal sequelae in the infant is required. Pregnancies are considered immediately reportable AEs (within 1 working day) and are to be documented in the e-CRF.

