- Pregnancy (β -human chorionic gonadotropin) tests for females of childbearing potential: Serum or urine samples will be obtained as specified in the Schedule of Events, page 10 and analyzed at the central laboratory (serum) or locally (urine). The urine pregnancy test on Day 1 must be negative before the first dose of study drug. A positive result during the study will result in immediate interruption of study drug.
- Follicle-stimulating hormone (FSH; Screening Period only): Blood sample for FSH will be measured for any suspected postmenopausal female with at least 12 months of continuous spontaneous amenorrhea. Serum FSH levels must be ≥ 40 mIU/mL to be considered postmenopausal.
- Plasma retinol and retinol binding protein: while this is to support an exploratory correlation with ophthalmological assessments, measurements may be used to support decisions made in relation with ophthalmological TEAe. Abnormal values may result in ad-hoc follow-up determinations, when associated with ophthalmological TEAe. Post-screening results will not be communicated to blinded staff, in order to maintain the study blind, unless required for emergency reasons.

Finally, clinical laboratory evaluations may be performed at other times if judged to be clinically appropriate by the Investigator.

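### Protocol Section 8.3 item 6 excepts IVF pregnancies from the 1-working-day report and from withdrawal, while Section 11.1.3.1 requires the report with no IVF exception and removal for any pregnancy that begins during the study

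*Protocol*

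**What the plan says.** **Section 8.3, item 6 (Protocol).** The trigger reads "If a female patient or a female partner of a male patient has a confirmed pregnancy (with the exception of a pregnancy resulting from"; the parenthesis then names IVF. Two duties follow: report to the Medical Monitor and the sponsor within 1 working day of discovery, and withdraw the patient. A separate sentence covers follow-up and carries no exception: "Pregnancy, whether in a patient or in a partner of a patient should be followed up until conclusion". The closing paragraph of 8.3 adds: "Upon withdrawal, no further dosing should be performed for these patients".

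**Section 11.1.3.1 (Protocol).** On removal: "If a patient or a female partner of a patient becomes pregnant during the study, the patient will be removed from the study", with no further study medication. On reporting: "Pregnancies are considered immediately reportable AEs (within 1 working day) and are to be documented in the e-CRF". Neither sentence mentions IVF.

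**Section 11.2 (Protocol).** On pregnancy tests: "A positive result during the study will result in immediate interruption of study drug". This does not depend on how conception occurred.

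**Section 11.1.1.3 (Protocol).** Two separate codes exist for action taken with study drug. Dose Interrupted is "Study drug administration interrupted in response to an AE" and Drug Withdrawn is "Study drug administration permanently discontinued in response to an AE".

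The SAP (Section 3.6) only summarises childbearing status and pregnancy test results. It sets no withdrawal or reporting rule for pregnancy.

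**The concern.** Two sections of one protocol give different instructions for the same event. A site that looks up withdrawal in Section 8.3, the natural place to look, is told that an IVF pregnancy falls outside both the urgent report and withdrawal. A site that looks in the SAE reporting section is told to do both.

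The subject is a safety rule. Exclusion 1 bars pregnant women because retinoids may be teratogenic, and Section 5.4.3.2 records teratogenicity of fenretinide in rats and rabbits at 800 mg/kg/day. Neither reason depends on how the pregnancy arose. Section 8.3 is also awkward on its own terms. It wants every pregnancy followed to its conclusion, yet it excepts some from the notification that would normally start that follow-up.

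**Working it through.** No published figure is involved. The check is to set the rules side by side, and then to see what the Section 11.2 interruption covers.

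**Step 1: reach of the exception.** In 8.3 item 6 the parenthesis comes after both subjects (female patient; partner of a male patient) and before both duties (report; withdraw). Grammatically it limits the trigger for all of them.

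**Step 2: an IVF pregnancy that begins during the study.**

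| Duty | Group | 8.3 item 6 | 11.1.3.1 |
|---|---|---|---|
| Report in 1 working day | Female patient | excepted | required |
| Report in 1 working day | Partner | excepted | required |
| Withdraw | Female patient | excepted | required |
| Withdraw | Partner (male patient leaves) | excepted | required |
| Follow to outcome | Both | required | required |

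That is 2 duties × 2 groups = 4 combinations, and all 4 differ. Follow-up differs in neither group.

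**Step 3: a partner already pregnant at entry.** Inclusion 12 admits these male patients. Removal under 11.1.3.1 applies only to a pregnancy that begins during the study, so withdrawal does not conflict. The report conflicts only if the reporting sentence is read as covering every pregnancy. At most 1 of the 2 duties differs.

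**Step 4: what Section 11.2 covers.** It interrupts drug in a tested (female) patient. It orders neither a report nor withdrawal, and it does not reach a partner's pregnancy. Its protection depends on how much dosing is left at each test. Cycle *k* starts on Day 28(*k* − 1) + 1 and doses for 21 days, so Cycle 6 runs from Day 141 to Day 161. The Schedule of Events has urine tests after the first dose on Days 21, 49, 77, 105, 161 and 189.

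| Test day | Full cycles still to come | Dosing days still to come (× 21) |
|---|---|---|
| 21 | 5 | 105 |
| 49 | 4 | 84 |
| 77 | 3 | 63 |
| 105 | 2 | 42 |
| 161 | 0 | 0, plus at most that day's dose |
| 189 | 0 | 0 |

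Four of the six tests can stop later dosing. Day 161 can stop at most the last dose, and Day 189 can stop none.

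**Step 5: is the stop final without 11.1.3.1?** Section 11.2 speaks of interruption, which 11.1.1.3 codes apart from permanent discontinuation, and within 8.3 it is withdrawal that ends dosing. However, Section 8.4 lets the patient, investigator or sponsor discontinue treatment at any time in the patient's interest. Section 8.4.1 also uses the word interrupted loosely, in a stopping rule that includes withdrawal from the study. A final stop is therefore available by discretion, though 8.3 does not mandate it for an IVF pregnancy.

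**The case against.** The strongest reply is that no site is forced into a breach. Section 8.3 leaves IVF pregnancies out of a duty but does not forbid reporting or withdrawing, so a site that follows 11.1.3.1 satisfies both sections. This is right, and it limits the harm to sites that act on 8.3 alone. It does not reconcile the texts, because 8.3 states an exception on purpose and nothing tells the site to override it.

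Second, the event is very rare. For female patients that stands: inclusion 11 requires highly effective contraception plus a second method. It is weaker for partners, because inclusion 12 lets male patients with documented sterilization waive contraception. On the other hand, the animal finding gives no direct evidence of risk through a male patient.

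Third, the counts in Steps 2 and 3 are counts of clauses, not of patients or risk. That also stands.

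Three stronger readings are tempting and not supported:

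- *The protocol lets a woman with an IVF pregnancy stay on drug.* It does not. Section 11.2 interrupts dosing on a positive test, and 11.1.3.1 removes her.
- *Only 11.1.3.1 can make the stop final.* Section 8.4 offers a discretionary route, and the codes in 11.1.1.3 record the action taken rather than set a dosing rule.
- *Six post-dose tests back the interruption.* Only those on Days 21, 49, 77 and 105 do, plus at most the last dose on Day 161.

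**Conclusion.** The inconsistency is real and should be corrected. For an IVF pregnancy that begins during the study, 8.3 excepts the report and withdrawal in both groups, 11.1.3.1 requires them in both, and no text reconciles the two. This rests on reading the parenthesis where it stands. If it was meant for partners only, which the text does not say, the conflict remains, because 11.1.3.1 names female partners.

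The consequence is small: a possibly late or missing pregnancy report, and unclear withdrawal status. Drug interruption for a female patient and follow-up to outcome are not excepted. No endpoint, analysis or sample size is affected. It merits correction because it sits in a pregnancy-safety rule for a drug the protocol itself reports as teratogenic in animals, and because wording alone cures it.

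**What to change.** Reword Section 8.3 item 6 so that:

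1. every pregnancy in a patient or partner, however conceived, is reported within 1 working day and followed to outcome;
2. any pregnancy in a female patient, however conceived, permanently stops study drug and leads to withdrawal.

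If the sponsor wants to keep an IVF exception, limit it to withdrawal of a male patient for a partner's pregnancy and state the same exception in 11.1.3.1. If not, delete the parenthesis. That alone removes the IVF conflict and leaves 11.1.3.1 untouched, although item 2 would still be worth adding to make the stop explicit.

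Cost: a wording amendment, with no new test or visit, and a few more pregnancy reports. Under Section 16.2 a changed withdrawal rule would probably be a substantial amendment needing regulatory and IRB/IEC approval. Bare deletion might be argued to be a clarification, but that classification is for the sponsor to make. Bundling the change with the next amendment keeps the burden low.
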